| Statistical Considerations: | The analysis of demographic characteristics (age, gender, tobacco abuse history and ethnicity) and baseline characteristics, including weight change, performance status, and histologic subtype, will primarily be descriptive. Kaplan-Meier estimates and survival curves for PFS, TTP and overall survival will be calculated. Secondary endpoints include response rates, clinical benefit rate (CR + PR + SD), toxicities and reversibility of toxicities) will also be estimated along with exact 95% binomial confidence intervals |
| Estimated Enrollment Period: | 30 months |
| Estimated Last Subject Enrollment Date: | June 15, 2020 |

1. INTRODUCTION

1.1 Background

Metastatic pancreatic adenocarcinoma carries a dismal prognosis with median survival rates of 3-6 months in those untreated. Over the past decade, despite oncologic advancements, there has been little influence on the long-term survival of these patients. Single agent gemcitabine was primarily used to improve disease related symptoms associated with advanced pancreatic adenocarcinoma, but it had minimal impact on survival. Over the last five years, more aggressive combination chemotherapy regimens such as gemcitabine and nab-paclitaxel and FOLFIRINOX (5-fluorouracil, leucovorin, oxaliplatin and irinotecan) have emerged proving more efficacious compared to gemcitabine alone and yielding a survival advantage. The MPACT study compared gemcitabine and nab-paclitaxel to gemcitabine alone in patients with untreated metastatic pancreatic adenocarcinoma and demonstrated a significant increase in survival with the combination regimen (8.5 months in the gemcitabine plus nab-paclitaxel arm versus 6.7 months in the gemcitabine arm; HR 0.72 (95% CI: 0.62, 0.84); p < 0.0001)¹. The PRODIGE study assessed first line treatment with FOLFIRINOX versus gemcitabine demonstrating improved survival with multi-agent chemotherapy. The median overall survival was 11.1 months compared to 6.8 months in the gemcitabine arm (HR for death, 0.57; p<0.001)². In November 2015, the FDA approved nanoliposomal irinotecan in combination with 5-fluorouracil (5-FU) and leucovorin as second line therapy for metastatic pancreatic adenocarcinoma in patients that had progressed following a gemcitabine based regimen. The addition of nanoliposomal irinotecan to 5-FU and leucovorin demonstrated a 2 month survival benefit compared to those treated with 5-FU and leucovorin alone³. Prior to this study, there was little objective evidence supporting second-line therapy offering patients a survival advantage. A few trials (mainly phase II) that studied treatment in the second line setting suggested limited benefit in select patients⁴⁻⁶. Indeed, consensus national guidelines now consistently support the role of second line therapy for otherwise fit patients (NCCN Guidelines as reference) and for patients whose performance status remains optimal, third line treatment can be considered. Despite the clinical use of these therapies, the median survival for patients with metastatic pancreatic adenocarcinoma continues to be less than 1 year substantiating the need for more effective treatments.

TAS-102 (Lonsurf[®]) is a combination drug of an oral nucleoside, trifluridine, and thymidine phosphorylase inhibitor, tipiracil hydrochloride. The nucleoside incorporates into DNA eliciting an anti-tumor effect and the thymidine phosphorylase inhibitor prevents enzymatic breakdown of the drug resulting in increased trifluridine bioavailability. It was FDA approved for use in patients with refractory metastatic colorectal cancer after progression on two or more standard chemotherapy regimens⁸. TAS-102 demonstrated a survival benefit despite all patients having being treated previously with 5-FU, which supports an alternative mechanism of action overcoming chemoresistance. TAS-102's efficacy is currently being investigated in other gastrointestinal cancers, specifically, metastatic gastric cancer refractory to standard therapies. Given the cross reactivity of many chemotherapy agents along the GI cancer spectrum (i.e., antimetabolites, platinums, topoisomerase inhibitors), the mechanism of action and chemical backbone of TAS-102 make it an attractive option to explore this agent in advanced pancreatic adenocarcinoma.

This protocol intends to study the activity and tolerability of TAS-102 in the treatment of metastatic or locally advanced unresectable pancreatic adenocarcinoma after progression on or intolerance to first or second line chemotherapy.

1.2 TAS-102 (Lonsurf[®]) Cancer Therapy

Each treatment cycle will be 28 days in duration. One treatment cycle consists of the following:

Days 1 through 5: TAS-102 ($35 \text{ mg/m}^2/\text{dose}$) orally 2 times daily with the first dose administered in the morning of Day 1 of each cycle and the last dose administered in the evening of Day 5. TAS-102 is to be taken within 1 hour of the morning and evening meal.

Days 6 through 7: Rest

Days 8 through 12: TAS-102 (35 mg/m²/dose) orally 2 times daily with the first dose administered in the morning of Day 8 of each cycle and the last dose administered in the evening of Day 12. TAS-102 is to be taken within 1 hour of the morning and evening meal.

Days 13 through 28: Rest Subjects should take study medication (TAS-102) with a glass of water within 1 hour after completion of their morning and evening meals.

1.3 Clinical Experience

TAS-102 is FDA approved for the treatment of metastatic colon cancer after progression on multiple lines of therapy including EGFR inhibitors in KRAS/NRAS wild-type patients. It has not yet been studied in pancreatic adenocarcinoma.

1.4 Rationale for Regimen/Doses/Schedule

The study will use the same dose of TAS-102 that is FDA approved for the use in metastatic colon cancer. It has previously been shown to be efficacious in patients that have been treated with 5-fluorouracil.

2. OBJECTIVES AND ENDPOINTS

2.1 Primary

• To determine progression free survival (PFS). The primary endpoint, PFS, is defined as the duration of time from study entry to time of progression or death or the date of last contact, whichever occurs first.

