4. REGISTRATION PROCEDURES

All consented subjects must be entered into the University of Florida's Clinical Trial Management System (OnCore) prior to assignment of a subject identification number. The study team must submit the completed study specific eligibility checklist, supporting source documentation and a copy of the signed informed consent document(s) to the UFHCC Project Management Office (PMO: [contact]) or their assigned Project Manager. Unsigned eligibility checklists or eligibility packets with missing or incomplete information may be returned to the study team. Upon receipt of a completed eligibility packet, the designated Project Manager will review the source to verify eligibility and assign a subject number. If eligibility cannot be confirmed, the project manager will query the site for clarification or additional documents as needed. Subjects failing to meet all study eligibility requirements will not be able to participate in the trial. Subjects who are not initiated on study drug, but sign informed consent and undergo at least some of the screening procedures will be considered screening failures. A record of these subjects will be maintained by the study site.

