5. STUDY TREATMENT

All subjects entering the screening phase will receive a unique subject number. This number will be used to identify the subject throughout the study. Subjects withdrawn from the study will retain their subject number.

5.1 Treatment Schedule/Administration:

Treatment must begin within 28 days of the date the subject is entered into the CTMS (OnCore). Upon confirmation of eligibility and provision of subject study number, subjects will receive TAS-102 at the following dose and schedule. The number of tablets of each strength that are needed for the 35 mg/m² dose per BSA level is shown in Table 1.

| TAS-102 | BSA ^a | Dosage in | Total daily | Tablets per dose | |
|----------------------|-------------------|------------|-------------|------------------|-------|
| Dose | (m ²) | mg | dose (mg) | _ | |
| (2x daily) | | (2x daily) | | 15 mg | 20 mg |
| 35 mg/m ² | < 1.07 | 35 | 70 | 1 | 1 |
| | 1.07 - 1.22 | 40 | 80 | 0 | 2 |
| | 1.23 - 1.37 | 45 | 90 | 3 | 0 |
| | 1.38 - 1.52 | 50 | 100 | 2 | 1 |
| | 1.53 - 1.68 | 55 | 110 | 1 | 2 |
| | 1.69 - 1.83 | 60 | 120 | 0 | 3 |
| | 1.84 - 1.98 | 65 | 130 | 3 | 1 |
| | 1.99 - 2.14 | 70 | 140 | 2 | 2 |
| | 2.15 - 2.29 | 75 | 150 | 1 | 3 |
| | ≥2.30 | 80 | 160 | 0 | 4 |
| | | | | | |

 Table 1. Dose Calculations Based off BSA

a Calculate body surface area (BSA) to 2 decimal places.

Each treatment cycle will be 28 days in duration. One treatment cycle consists of the following:

Days 1 through 5: TAS-102 ($35 \text{ mg/m}^2/\text{dose}$) orally 2 times daily with the first dose administered in the morning of Day 1 of each cycle and the last dose administered in the evening of Day 5.

Days 6 through 7: Rest

Days 8 through 12: TAS-102 (35 mg/m²/dose) orally 2 times daily with the first dose administered in the morning of Day 8 of each cycle and the last dose administered in the evening of Day 12.

Days 13 through 28: Rest

The patient must be instructed in the handling of study medication as follows:

- To store the study medication at room temperature
- To only remove from the study medication kit the amount of tablets needed at the time of dosing
- Not to remove doses in advance of the next scheduled dosing
- To make every effort to take doses on schedule
- To take study medication within 1 hour after completing a meal (morning and evening meals) with a glass of water per the dose schedule
- If the patient vomits after taking study medication, the patient should not take another dose.

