6 TREATMENT DISCONTINUATION

6.1 Removal of Subjects From Study

Subjects who discontinue participation in the clinical study on their own or subjects who are withdrawn by the investigator, for reasons other than completion of treatment, disease progression or toxicity, will be defined as premature withdrawals.

Subjects who are not initiated on study drug, but sign informed consent and undergo at least some of the screening procedures will be considered screening failures. A record of these subjects will be maintained by the study site.

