Progressive disease (PD): unequivocal appearance of one or more new malignant lesions. Unequivocal progression of existing non-target lesions. Although a clear progression of nontarget lesions only is exceptional, in such circumstances, the opinion of the treating physician should prevail and the progression status should be confirmed later on by a review panel (or study chair/primary investigator).

Evaluation of best overall response

The best overall response is the best response recorded from the start of the treatment until disease progression/recurrence (taking as reference for progressive disease the smallest measurements recorded since the treatment started). In general, the subject's best response assignment will depend on the achievement of both measurement and confirmation criteria.

Table 5 provides a summary of the overall response status calculation at each time point for patients who have measurable disease at baseline. When subjects have non-measurable (therefore non-target) disease only, Table 6 should be used.

| Target Lesion | Non-target Lesions | New Lesions | Overall Response |
|----------------------|--------------------------------|-------------|---------------------|
| CR | CR | No | CR |
| CR | Non-CR/non-PD | No | PR |
| PR | Non-PD or not at all evaluate | No | PR |
| SD | Non-PD or not at all evaluated | No | SD |
| Not at all evaluated | Non-PD | No | Inevaluable |
| PD | Any | Yes or No | PD |

Table 5. Evaluation of Best Overall Response: Subjects with Target Disease, with or without Non-target Disease

| Target Lesion | Non-target Lesions | New Lesions | Overall Response |
|---------------|--------------------|-------------|---------------------|
| Any | PD | Yes or No | PD |
| Any | Any | Yes | PD |

Table 5. Evaluation of Best Overall Response: Subjects with Target Disease, with or without Non-target Disease

Table 6. Evaluation of Best Overall Response: Subjects with Non-target Disease Only

| Non-target Lesions | New Lesions | Overall Response |
|--------------------|-------------|-----------------------------|
| CR | No | CR |
| Non-CR/ non-PD | No | Non-CR/ non-PD ^a |
| Not all evaluated | No | Inevaluable |
| Unequivocal PD | Yes or No | PD |
| Any | Yes | PD |

^a'Non-CR/non-PD' is preferred over 'stable disease' for non-target disease since SD is increasingly used as endpoint for assessment of efficacy in some trials so to assign this category when no lesions can be measured is not advised.

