8.4 Confirmation

In non-randomized trials where response is the primary endpoint, confirmation of PR or CR must be confirmed by repeat measurements that should be performed no less than 4 weeks after the criteria for response are first met. In this trial, as overall response rate is a secondary endpoint, confirmation of response in the form of a PR or CR will occur 8 weeks after the criteria for response are first met, since restaging imaging per the protocol will be performed every other chemotherapy cycle (ie every 8 weeks).

In randomized trials or studies where the primary endpoints are stable disease or progression, confirmation of response is not required. Elimination of the requirement for response confirmation may increase the importance of central review to protect against bias, particularly in studies which are not blinded.

In the case of SD, follow-up measurements must have met the SD criteria at least once after study entry at a minimum interval of 6-8 weeks.

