12.3 Primary and Secondary Endpoint Efficacy Analysis

The primary endpoint to this study will be to determine progression-free survival following TAS-102 therapy. Kaplan-Meier mean estimates and survival curves of progression-free survival rates will be calculated.

A secondary endpoint of this study will be overall survival/TTP following treatment with TAS-102. Kaplan-Meier estimates and survival curves will be calculated. Other secondary endpoints include response rates, clinical benefit rate (CR + PR + SD), toxicities, reversibility of toxicities, and compliance with intended treatment will also be estimated along with exact 95% binomial confidence intervals.

No multiplicity will be adjusted for the secondary endpoints. All data analysis will be conducted in reproducible fashion and the results will be reported regardless of the statistical significance.

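### Does the undefined starting point of the PFS clock bias the primary comparison in favour of TAS-102?

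*Combined protocol and SAP*

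**What the plan says.** The synopsis and section 2.1 give PFS as "defined as the duration of time from study entry to time of progression or death". No definition of study entry appears in the text available.

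Several places suggest the start of treatment. Section 12.3 sets out "to determine progression-free survival following TAS-102 therapy" and describes OS and TTP in the same way, as following treatment. Section 8.3 takes best overall response as "the best response recorded from the start of the treatment until disease progression/recurrence". Section 8.4 says that follow-up measurements for stable disease "must have met the SD criteria at least once after study entry at a minimum interval of 6-8 weeks", which fits a first on-study scan at Cycle 3.

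Other places allow an earlier date. Section 4 says "All consented subjects must be entered into the University of" Florida's trial management system (OnCore) before a subject number is assigned, and section 5.1 allows up to 28 days from that entry to treatment.

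On who is analysed, section 12.1 calls the primary comparison intent-to-treat but sizes it on 33 evaluable subjects who receive the same dose level. Sections 4 and 6.1 class consented but undosed subjects as screening failures once any screening has been done ("Subjects who are not initiated on study drug, but sign informed consent"). Section 6.3 replaces only subjects lost to follow-up before a first dose.

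**The concern.** OnCore entry is the only dated act that the protocol describes as a subject being entered. Suppose the PFS clock started there while the analysis kept only subjects who went on to dosing. Each analysed subject would then have had to reach the first dose, and the waiting time could add event-free time that the drug did not produce.

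The design is sensitive to this. The alternative is a median of 9 weeks against 6, so an average wait of 1 week is a third of the effect sought. The trial is single-arm, and its fixed historical reference has no stated time origin, so nothing guarantees that the lead-in cancels. With both the origin and the analysis set unstated, they could in principle be chosen after the results are known.

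**Working it through.** **The plan's own sample size.** Inputs from section 12.1: medians 6 and 9 weeks, exponential PFS, one-sided 0.10, 80% power, 24 months' accrual and about 30 months in total. Uniform accrual and 6 months' further follow-up are assumed. For the one-sample log-rank test,

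n = (z_α√v0 + z_β σ)² / (v1 − v0)², with v0 = 1.475, v1 = 0.983, σ² = 2.141.

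This gives (1.2816 × 1.2145 + 0.8416 × 1.4633)² / 0.4917² = 32.2, rounded up to 33. Allowing for 10% inevaluable, 33/0.9 = 36.7, rounded up to 37. Both stated figures reproduce.

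**The test under the null.** λ0 = ln 2 / 6 = 0.1155 per week. With complete follow-up O = 33, and E is λ0 times the summed PFS times. The test rejects when (E − O)/√E > 1.2816, that is, when E > 41.23. With no gap E is Gamma(33, 1), and the rejection probability is 0.083.

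**Worst case: every event in the gap excludes the subject.** The fixed lead-in assumed here is s weeks, and E becomes Gamma(33, 1) + 33 × 0.1155 × s.

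| Gap s (weeks) | Added to E | Gamma must exceed | False-positive rate |
|---|---|---|---|
| 0 | 0 | 41.23 | 0.083 |
| 0.5 | 1.91 | 39.32 | 0.137 |
| 1 | 3.81 | 37.42 | 0.213 |
| 2 | 7.62 | 33.60 | 0.435 |

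If every subject used the full 28 days, the rate would be about 0.90. The documents give no distribution of the gap, so all these gaps are assumptions within the permitted window.

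**How many gap events exclude a subject.** Under the null, 1 − exp(−0.1155) = 11% of subjects would have an event within 1 week of registration and 21% within 2 weeks. The table assumes that all of them drop out. Screening imaging may be up to 28 days before treatment (sections 7.1 and 7.2; section 8.1 has the same limit for baseline). The next scheduled scan is at Cycle 3, and none is required in between. A subject whose tumour grows unnoticed in the gap is therefore still dosed, and the growth counts against the baseline scan. Mainly deaths and clinical decline would be lost. Keeping the remaining gap events at their true dates, simulation with n = 33 gives:

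| Share of gap events that exclude the subject | 1-week gap | 2-week gap |
|---|---|---|
| 0% | 0.08 | 0.08 |
| 25% | 0.10–0.11 | 0.13 |
| 50% | 0.13 | 0.19–0.20 |
| 100% | 0.21 | 0.43 |

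**Readings with no inflation from this source.** The rate is 0.083 if the clock starts at first dose, and also if all registered subjects are kept with true event dates. If the 6-week reference already contains the same lead-in, the direction reverses: about 0.05, 0.03 and below 0.01 for 0.5, 1 and 2 weeks.

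All these figures date events continuously. Dating progression at 8-weekly scans is a separate matter and does not bear on the choice of origin.

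**The case for a change.** The strongest case for acting is that the primary endpoint's origin should be a named date, that naming it costs a few words, and that the margin is thin. In the worst-case model a gap of 0.18 weeks (about 1.3 days) uses up the test's conservatism, and 0.92 weeks (about 6.5 days) takes the rate to 0.20. The intent-to-treat label does not settle the matter either: scans and follow-up visits are tied to treatment, so undosed subjects would have few recorded outcomes.

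What stands is that the term is undefined and that pairing a pre-dose origin with a dosed-only set would be wrong. What does not stand is that the text points equally both ways. Section 3.2 speaks of patients becoming eligible to enter the study, whereas OnCore entry comes before eligibility is reviewed, and no passage links the OnCore record to PFS. Sections 8.3 and 12.3 run from treatment, and section 12.3 does so for OS and TTP as well as PFS. Nor is the waiting time event-free by construction, since radiographic progression in the gap need not stop a subject being dosed.

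**Conclusion.** No change follows. The plan leaves a term undefined, but no rule it states is shown to give a wrong result. An analyst would most naturally count from first dose in dosed subjects, and the false-positive rate is then about 0.08 against a nominal 0.10. Counting from registration with all registered subjects kept at true event dates gives the same rate. Only a mismatch of origin and analysis set, combined with a reference that has no lead-in, favours the drug. In that case the rate is 0.08 to 0.21 for a 1-week gap and 0.08 to 0.43 for 2 weeks, assuming exponential PFS, n = 33, continuous dating and the gap lengths shown.

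Replacing the stated intent-to-treat comparison with a treated set would be a trade-off rather than a correction. First dose needs no outcomes from undosed subjects. Registration may sit closer to a reference counted from registration or randomisation, but it needs outcomes for the undosed. The reference's own origin is not given in the documents, so neither choice can be shown to match it better.

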| | Days 8 through 12: TAS-102 (35 mg/m ² /dose) orally 2 times daily with the first dose administered in the morning of Day 8 of each cycle and the last dose administered in the evening of Day 12. TAS-102 is to be taken within 1 hour of completion of morning and evening meals. |
| | Days 13 through 28: Rest |
| | Treat subjects on protocol until progression of disease on the study drug or intolerance after pre-specified dose reductions or subject desire to come off treatment |
| | Primary Endpoint: |
| | • The progression free survival (PFS) defined as the duration of time from study entry to time of progression or death or the date of last contact, whichever occurs first. |
| | Secondary Endpoints: |
| Enapoints: | The objective response rate (ORR) by RECIST 1.1 criteria The Clinical Benefit Rate (CR + PR + SD) The time to progression (TTP) Overall survival (OS) The sofatu profile and tolerability in this perpulation |
| | The safety profile and tolerability in this population Compliance with intended treatment |

| Study Design: | Open-label, non-randomized, sequentially enrolling single arm phase II trial |
|------------------------|---|
| Accrual Goal: | 33 subjects |

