6.2 Study Treatment Discontinuation

Study treatment will be withheld under the following circumstances::

- Grade 4 neutropenia (ANC less than 500/mm³ or febrile neutropenia), until ANC is resolved to greater than 1500/mm³ or febrile neutropenia is resolved
- Grade 4 thrombocytopenia or grade 3 thrombocytopenia with bleeding (platelets less than 50,000/mm³), until platelet count resolved to greater than or equal to 75,000/mm³
- Other grade 3 or 4 non-hematologic toxicity, until the adverse reaction has resolved to Grade 0 or 1

A subject will be discontinued from protocol therapy under the following circumstances:

- Any adverse event which, in the Investigator's opinion, requires termination of the study medication.
- Disease progression, unless at the discretion of the Principal Investigator (in collaboration with any co-sponsors or collaborators) determines continued treatment with study drug is appropriate.
- Substantial non-compliance (>25% of missed doses with the exception of dose delays and dose modifications per protocol, or dose-related instructions from research team staff due to adverse events), with the requirements of the study.
- The subject presents with a beta-HCG test consistent with pregnancy and is confirmed to be pregnant. Pregnancy will be reported along the same timelines as a serious adverse event.
- The subject uses illicit drugs or other substances that may, in the opinion of the Investigator, have a reasonable chance of contributing to toxicity or otherwise interfering with the study or its results.

- The development of a second malignancy that requires treatment, which would interfere with this study.
- The subject is lost to follow-up.
- Development of an intercurrent illness or situation which would, in the judgment of the investigator, affect assessments of clinical status and study endpoints to a significant degree.

The Investigator will make every reasonable effort to keep each subject in the study unless it is in the subject's best interests to discontinue participation. If a subject is removed from the study or declines further participation, all End of Treatment evaluations should be performed if the subject is willing and able to be assessed. A description of the reason(s) for withdrawal from the study must be recorded on the case report form (CRF). The Investigator should also ensure that all subjects are followed up for survival status and progression (as applicable) after the End of Treatment Visit.

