g. h. CT of the chest, abdomen and pelvis or CT of the chest and MRI of the abdomen and pelvis are allowed. Consistent imaging modality should be used throughout the study. Imaging should be performed every 8 weeks (+/- 7 days) beginning with Cycle 3 until disease progression.

H&P is required at 30 days (+7 days) following the last dose of study drug. Additional H&Ps are required as needed to follow ongoing AEs.

Adverse events should be followed for 30 days after the last dose of protocol therapy or until the initiation of subsequent treatment. AEs continuing > 30 days should be monitored until resolution.

Subjects or providers should be contacted every 3 months to assess survival status and subsequent therapies.

TAS-102 (Lonsurf[®]) is administered orally twice daily within one hour of completion of morning and evening meals on Days 1 through 5 and Days 8 through 12 of each 28-day cycle.

For CBC w/diff to be obtained at Day 15 of each cycle, notify the investigator if any of the following parameters are observed m. in the lab results: 1) ANC \leq 500 µL, 2) platelets < 50 thou/mm³, or 3) Hgb < 7 g/dL.

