7.5 Follow up/Survival

Please refer to Table 4 located in Section 7.1.

For the purpose of this study, subjects will be seen in follow-up at least every three months until one year after the completion of study treatment. Follow-up evaluations may consist of the interim medical history, physical examination, imaging, CBC, or comprehensive metabolic panel. Any X-rays, CT or MRI scans, or other studies (such as PET scans, bone scans, biopsies, etc.) will be done as clinically indicated and up to the discretion of the treating physician.

After this one-year follow-up period is over, subjects will be continued to be followed for survival until death, withdrawal, or lost to follow up. If subjects are lost to follow-up, every effort will be made at least quarterly to attempt to locate that subject and to determine their health status.

For subjects that come off protocol for reasons other than progressive disease, then CT or MRI scans will be performed every 8 weeks to document disease progression. until disease progression is shown or another anti-cancer therapy is initiated.

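### Primary PFS runs to an undefined date of last contact, with no rule for new therapy or missed scans, so time without scheduled scans can count as progression-free

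*Combined protocol and SAP*

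**What the plan says.** Section 2.1 ends primary PFS at "progression or death or the date of last contact, whichever occurs first". The synopsis gives the same definition: PFS runs "from study entry to time of progression or death or the date of last contact, whichever occurs first". Neither says whether last contact is an event or a censoring time.

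The analysis sections do not settle it. Section 12.1 describes an intent-to-treat comparison with a historical reference and names the one-sample log-rank test for the sample size. Section 12.3 names Kaplan-Meier means and curves. Neither has a censoring rule. Section 6.3 treats loss to follow-up as missing data without imputation, and does not say whether such subjects are censored or left out.

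On imaging, the Table 4 notes in Section 7.1 say "Imaging should be performed every 8 weeks (+/- 7 days) beginning with Cycle 3 until disease progression". Section 7.5 says that subjects who come off protocol without progression have 8-weekly scans "until disease progression is shown or another anti-cancer therapy is initiated". Contact goes on: "Subjects or providers should be contacted every 3 months to assess survival status and subsequent therapies" (Table 4 notes), and after the first year subjects are "followed for survival until death, withdrawal, or lost to follow up" (Section 7.5).

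Other passages bear on detection. Section 7.5 says "subjects will be seen in follow-up at least every three months until one year after the completion of study treatment", with imaging in that period at the physician's discretion. Section 6.2 asks that "all subjects are followed up for survival status and progression (as applicable) after the End of Treatment Visit". Section 8.3 asks for objective progression to be documented after treatment stops. Two PFS details are settled: palliative radiation to a single lesion (5.3.2) and the dating of equivocal progression (8.3).

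**The concern.** Progression can only be dated when someone looks for it. If scheduled scans stop at a switch but the PFS clock runs to last contact or death, the gap counts as progression-free. The trial has one open-label arm and is judged against a 6-week reference median, so no control arm shares the distortion. Early leavers are the exposed group. On-study imaging starts with Cycle 3, about week 8, so a subject who leaves at week 4 may have only a baseline scan. A switch is plausible: one prior regimen is enough for entry (3.2), and Section 1.1 accepts that third-line treatment can be considered. At stake are the one-sided 0.10 test and the Kaplan-Meier mean that 12.3 will report. A rule chosen after the data are seen could affect either.

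**Working it through.** **The plan's own figure.** Inputs from 12.1: medians of 6 and 9 weeks, exponential, one-sided 0.10, power 80%. With full follow-up under the alternative, the expected null cumulative hazard per subject is v0 = 9/6 = 1.5, the event probability is v1 = 1, and the standard deviation of their difference is 1.5. Then

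n = (√1.5 × 1.2816 + 1.5 × 0.8416)² / (1.5 − 1)² = 32.08, so 33, and 33/0.9 = 36.7, so 37.

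Both stated figures reproduce. The point does not concern the sample size.

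**What one switcher adds.** The null hazard is ln 2/6 = 0.1155 per week. A subject with an event at week t adds 0.1155t − 1 to expected minus observed events (positive favours the drug). A subject censored at a baseline scan adds 0. Break-even is t = 6/ln 2 = 8.66 weeks.
- Progression found at week 8: 0.924 − 1 = −0.08.
- Progression found at week 17 (13 weeks after a week-4 switch): 1.96 − 1 = +0.96.
- Never found, death at 4 + m/ln 2 weeks on average: m = 13 gives week 22.8 and +1.63; m = 26 gives week 41.5 and +3.79.

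The sign therefore depends on when progression is found.

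**Simulation.** n = 33, null median 6 weeks, reject if (E − O)/√E > 1.2816, 60,000 trials per cell, 24 months of accrual and cut-off at 30 months. Assumed, not in the documents: the number of switchers, the switch at week 4 with only a baseline scan, and residual median survival m = 13/26 weeks, loosely taken from the 3-6 months for untreated disease in 1.1. After the switch, progression follows the null hazard. Type I error for m = 13/26:

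| Later progression | Exactly 3 of 33 | Exactly 1 of 33 | Average 3 of 33, drawn at random from null subjects event-free at week 4 |
|---|---|---|---|
| Found 8-weekly | 0.11/0.13 | 0.09/0.10 | 0.07/0.09 |
| Found 13-weekly | 0.14/0.17 | 0.10/0.11 | 0.10/0.13 |
| Never found | 0.28/0.55 | 0.13/0.21 | 0.23/0.46 |
| Censored at last scan | 0.08 | 0.08 | 0.05 |

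Without switchers it is 0.08. A different switching model (10% switching, progression never found, last contact treated as censoring) gives 0.16-0.35. If last contact is counted as an event, the range is 0.08-0.25.

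**Reversal.** Suppose the switchers are subjects who would have progressed in weeks 4-8 and are scanned at week 8. Adding 3 such subjects to 30 null subjects gives about 0.07 under the written rule, against 0.08 with last-scan censoring. Drawing an average of 3 of 33 from the null population gives about 0.10 against 0.12. With 13-weekly detection in the drawn version, the written rule is again the higher (about 0.15-0.19).

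**Source of the excess.** With 3 of 33 and none found, removing only the last-contact credit lowers 0.28 to 0.23 and 0.55 to 0.35. With detection it changes the result by less than 0.01. At m = 13 most of the excess comes from deaths counted after an unscanned gap.

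**Kaplan-Meier mean, 3 of 33.** 8.6 weeks without switchers; 9.2/9.4 with 13-weekly detection; 9.9/11.2 if none is found; 8.6-8.7 with last-scan censoring.

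**The case against.** The strongest reply has four parts.

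1. *The wording does not always favour the drug.* This stands. A reader might infer that crediting time to last contact can only help TAS-102. The break-even at 8.66 weeks and the reversal above show otherwise: progression found at a week-8 scan counts slightly against the drug, while censoring at baseline removes the subject.

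2. *The fixed-number illustration is not a pure null.* This also stands in part. Switchers are event-free to week 4 by construction, so each brings 4 × 0.1155 = 0.46 expected events of credit before the definition plays any role. Part of the 8-week excess is therefore not due to the wording. In the random-draw version the 8-week cells stay below 0.10. In addition, only switchers have scan-dated progression in these runs; all other subjects progress at exact times. The figures show contrasts between rules, not operating characteristics of this trial.

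3. *Kaplan-Meier implies that last contact is a censoring date.* That is the natural reading, but it is the reading that credits unscanned time. It also does not cover deaths after a gap.

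4. *Section 7.5 is the specific rule for subjects off protocol, so it does not really conflict with Table 4.* The Table 4 note does not mention a switch. Still, one passage has a single stopping point and the other has two. Sections 6.2 and 8.3 ask for progression to be followed but set no scan schedule after a switch.

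**Conclusion.** The point holds in limited form. The primary endpoint lacks a censoring rule, and the follow-up passages allow time without scheduled scans to count as progression-free. The effect favours the drug when later progression is found late or not at all. With prompt 8-weekly detection it is small and can reverse.

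For 3 of 33 switching at week 4, type I error is about 0.14/0.17 with 13-weekly detection and 0.28/0.55 with none, against about 0.08 with last-scan censoring. These figures rest on an assumed number and time of switches and assumed survival. A reader might take 0.28 or 0.55 as the error rate of this trial. The documents do not support that: they give no switch rate, and they provide for visits at least every three months for a year, at which progression may be found. The stated 33 and 37 are unaffected.

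**What to change.** - In the synopsis and 2.1, define PFS as time from study entry to first RECIST 1.1 progression or death from any cause. Censor subjects with neither at the last evaluable tumour assessment, or at study entry if there is none after baseline. Use date of last contact for overall survival only.
- Fix one primary rule in advance for events after new anticancer therapy or after two or more missed assessments. Either count all progressions and deaths regardless of later therapy, which fits the intent-to-treat wording in 12.1, or censor at the last evaluable assessment before the switch or gap. Report the other option, and the switch counted as an event, as sensitivity analyses.
- State in 6.3 that subjects lost to follow-up are censored and stay in the intent-to-treat analysis.
- Reconcile the imaging passages in 7.5 and Table 4, so that the scans collected match the rule chosen. Counting all events depends on progression still being looked for after a switch.

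The cost is mainly wording, since the schedule already provides for scans and for recording subsequent therapies. The censoring option means fewer PFS events and possibly informative censoring. With random switchers censored at baseline, power at a 9-week median falls from 0.83 to 0.80 (average 1 of 33) or 0.74 (average 3). If switchers are those about to progress in weeks 4-8, type I error rises to 0.10 or 0.12. That is why the choice should be made in advance and the alternatives reported.
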